9.3. Randomisation

All patients who received a CT Lucia 601 at least 6 months ago will be contacted and asked for participation in our clinical trial. There will be no randomization necessary since we only plan one postoperative non-invasive visit without performing an invasive intervention or using a study drug. All patients will undergo the same technical examinations.

9.4. Withdrawal of participants

Subjects are free to discontinue participation in the investigation at any time, and without prejudice to further treatment. Subjects who discontinue the investigation should always be asked about the reason(s) for their discontinuation and about the

presence of any Adverse Event/Adverse Device Effect or Device Deficiency and, if possible, be assessed by an investigator. Adverse Event/Adverse Device Effect should be followed up.

Subjects may be withdrawn from investigation treatment and assessments at any time, at the discretion of the investigator.

Incorrectly enrolled subjects will be withdrawn from further investigation treatment and assessments. A subject may, however, continue the investigation under special circumstances (i.e. if continuation of investigation treatment or follow-up actions are necessary for the subject's safety and well-being, or if only a follow-up period remains, and the continuation of the investigation is not expected to be associated with any risk or discomfort for the subject).

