4. CLINICAL INVESTIGATION SUMMARY

Title	CT Lucia 601 IOL implantation in the sulcus
Reference Number (Acronym)	CLuS
Clinical phase	Post-marketing study (phase 4)
Objectives	To perform a retrospective investigation of the CT Lucia 601 IOL implantation in the sulcus

Endpoints	Primary endpoint: determine whether the CT Lucia 601 IOL can be used safely in the sulcus
Design	Non-commercial (academic with study grant), monocentric, post-interventional observational without use of a study drug
Data Collection	A single late-postoperative visit, scheduled ≥ 6 months after the vitrectomy See Study Flow Chart 7.3
Planned Clinical investigation Period	2019-2020
Clinical investigation population	Patients who had an implantation of the CT Lucia 601 lens
Number of Participants	100
Inclusion/Exclusion Criteria	
Inclusion criteria
 
 • Patients with an implantation of a CT Lucia 601 lens for different reasons: 
 ○ During vitrectomy to treat a complicated cataract surgery and had the implantation of a CT Lucia 601 IOL in the sulcus or patients ○ During phaco surgery with a posterior capsule tear that necessitated the implantation of the implant lens in the sulcus ○ Explantation of an in-the-bag lens and implantation of a CT Lucia 601 as replacement lens (e.g. to treat opacification of the implant lens or intolerance of the implant lens). • Age : > 18 years • Signed informed consent • Preoperative myopia less than 10 diopters • Implantation of the CT Lucia IOL at least six months earlier 
Exclusion criteria
 
 • History of uveitis • Ocular pathology or history that could influence the biometry of the effective lens position, such as ocular trauma with zonulolysis, congenital iris- or lens defects etc. • Any eye condition influencing the lens position (to be specified) according to the investigator
Device Name	CT LUCIA hydrophobic C-loop IOL: CT Lucia® 601P (hydrophobic acrylic with heparin coated surface)

Principle Intended Use	All devices are CE marked and used within their claimed intended use. In general, all devices are intended to be used during ophthalmic surgery.
Manufacturer Name	CT LUCIA 601P

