6. OBJECTIVES

The purpose of the study is to collect data that are parameters of post-IOL implantation safety:

- Questionnaire on subjective quality of vision
- Centration and anteroposterior position of the IOL (using biometry)
- Presence and quantification of any inflammation or pigment present in the anterior chamber (flare meter)
- Refractive outcome, with calculation of customized A-constant of the CT Lucia 601 IOL in-the-sulcus and quantification of higher-order aberrations (HOA)
- General safety-parameters:
 - Visual acuity
 - Intra-ocular pressure
 - Presence of macular edema or retinal nerve fiber layer (RNFL) thinning (SD-OCT)
 - Any adverse ophthalmic events

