8.3. Exclusion criteria

- History of uveitis
- Ocular pathology or history that could influence the biometry of the effective lens position, such as ocular trauma with zonulolysis, congenital iris- or lens defects etc.
- Any eye condition influencing the lens position (to be specified) according to the investigator

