13.4. Criteria for the termination of the clinical investigation

There will be only one postoperative visit to examine the patients, the clinical investigation will be terminated after this visit. No statistical interim analysis is planned.

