16.2. Clinical investigation plan violations, deviations and serious breaches

The Clinical investigator will not implement any deviation from the clinical investigation plan without agreement from the Sponsor, except where necessary to eliminate an immediate hazard to clinical investigation participants.

In the event that the Clinical investigator needs to deviate from the clinical investigation plan, the nature of and reasons for the deviation will be recorded in the CRF and notified to the Sponsor. If this necessitates a subsequent clinical investigation plan amendment, this will be submitted to the Sponsor for approval and then to the appropriate REC and Regulatory Authority for review and approvals as appropriate. It is Sponsor policy that waivers to the clinical investigation plan will not be approved.

In the event that a serious breach of GCP is suspected, this will be reported to the Sponsor immediately.

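### The open-ended lens-position exclusion in 8.3, with no withdrawal criteria in 9.4 and no analysis set in 13.7, leaves malpositioned eyes removable from the safety result

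*Combined protocol and SAP*

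**What the plan says.** All references are to the combined protocol and SAP.

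- **Aim.** Section 4 gives the primary endpoint as "Primary endpoint: determine whether the CT Lucia 601 IOL can be used safely in the sulcus". No rate or threshold is attached. Section 6 lists lens centration and anteroposterior position among the safety parameters.
- **Exclusion.** The third criterion in section 8.3 is "Any eye condition influencing the lens position (to be specified) according to the investigator". It gives no list of conditions, no date limit and no source record.
- **Timing.** Implantation must lie at least six months back (8.2). Section 13.4 states "There will be only one postoperative visit to examine the patients", and section 9.2 places the consent signature at that hospital appointment. No section says when the ocular criteria are checked.
- **Withdrawal.** Section 9.4 says "Subjects may be withdrawn from investigation treatment and assessments at any time, at the discretion of the investigator", and "Incorrectly enrolled subjects will be withdrawn from further investigation treatment and assessments". It then adds "A subject may, however, continue the investigation under special circumstances".
- **Analysis.** Section 13.7, although titled for inclusion in the analysis, says only which patients will be approached. No section says whether measurements from a withdrawn subject are used.

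**The concern.** An exclusion criterion should depend on facts fixed before the outcome. Here it concerns influences on lens position, and lens position is one of the outcomes. For a lens implanted months earlier, a condition that moves it may have developed after surgery, as part of what the safety question asks about. Nothing in 8.3 separates such a condition from one that was present before implantation.

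The judgement rests with the centre that chose and implanted the lens. Section 5 reports that this centre already assessed centration and position at postoperative visits and found them very good. No bad faith is needed: case-by-case decisions made with the result in view tend to follow it. Eyes lost this way come from the malpositioned group, so a malposition proportion would be biased downward, toward a conclusion of safe use.

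**Working it through.** **1. Can a post-implantation condition meet the exclusion?** Yes, on its wording. Section 8.3 does not say when the condition must have been present, leaves it to be specified, and gives the decision to the investigator. Section 8.2 guarantees at least six months in which one could arise.

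**2. Can the decision be made with the lens position known?** Yes, by two routes. Before the study visit, the centre may know the position from routine follow-up (section 5). At or after the visit, the study biometry is available, and a subject then judged ineligible falls under the rule for incorrect enrolment in 9.4, or under its open discretion.

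**3. Is the eye then kept in the analysis?** The plan does not say. Section 9.4 covers treatment and assessments only, and 13.7 names no analysis population.

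**4. What would catch it?**

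| Section | Safeguard | What it leaves open |
|---|---|---|
| 9.4 | Discontinuing subjects are asked for reasons and adverse events | Does not keep the eye in the analysis |
| 12.3 | eCRF changes are logged and time-stamped | Covers only eyes already entered |
| 13.5 | Missing data reported with reasons where available; missingness modelled on baseline variables | Baseline models cannot show dependence on the result itself |
| 13.6 | Final statistical plan agreed before data lock | Could define the set, but is not required to |
| 16.2 | Deviations recorded and notified to the sponsor | Applying 8.3 as written is not a deviation |
| 19.5 | Safety issues recorded on the CRF | Recording is not inclusion in the analysis |

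Each may leave a trace. None requires the eye to be counted.

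**5. How large could the effect be?** The plan has no figure to reproduce: the 100 patients in 8.1 come without a calculation, and 13.2 cites only the exploratory nature of the trial. The following is an illustration.

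Inputs: 100 implanted eyes, one per patient (8.1; one eye per patient is assumed); M malpositioned eyes, with M = 3, 5 or 10 (assumed, as the documents give no rate); r of them dropped and not replaced (assumed).

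The reported proportion is x/n with x = M − r and n = 100 − r. The exact two-sided 95% limits are the 0.025 quantile of Beta(x, n − x + 1) and the 0.975 quantile of Beta(x + 1, n − x). For x = 0 the upper limit is 1 − 0.025^(1/n).

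| M | r | x/n | Proportion | 95% CI |
|---|---|---|---|---|
| 3 | 0 | 3/100 | 3.0% | 0.6 to 8.5 |
| 3 | 3 | 0/97 | 0% | 0 to 3.7 |
| 5 | 0 | 5/100 | 5.0% | 1.6 to 11.3 |
| 5 | 2 | 3/98 | 3.1% | 0.6 to 8.7 |
| 5 | 5 | 0/95 | 0% | 0 to 3.8 |
| 10 | 0 | 10/100 | 10.0% | 4.9 to 17.6 |
| 10 | 5 | 5/95 | 5.3% | 1.7 to 11.9 |
| 10 | 10 | 0/90 | 0% | 0 to 4.0 |

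For M = 5, all dropped: 1 − 0.025^(1/95) = 0.038. That limit lies below the 5.0% found when every eye is kept. With M = 3 the limit of 3.7% still lies above 3.0%. Partial removal shifts the estimate, but in the cases shown the interval still covers the full-data value.

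**The case against.** The strongest reply is that the plan nowhere tells anyone to remove a malpositioned eye, and that section 9.4 is standard wording carried over from treatment trials. Several stronger readings are tempting, and the documents do not support them.

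- *An abnormal lens position itself triggers withdrawal.* Section 8.3 excludes a condition that influences position, which is a cause and not the position found. The examples in the preceding criterion are trauma with zonulolysis and congenital defects, which points to pre-existing disease. What stands is that a malposition could be taken as evidence of an unspecified, undated condition.
- *Withdrawal under 9.4 deletes the data.* It does not. The text concerns assessments, and for incorrectly enrolled subjects only further ones. The gap is the silence of 13.7.
- *Eligibility and outcome are necessarily seen together at the visit.* Only the consent signature is placed there. Ocular eligibility could be screened from records before the telephone calls. The plan does not require this, and earlier screening alone would not help if the position is already known from follow-up.
- *Nothing in the plan could detect it.* This is too strong, given the partial safeguards tabulated above.
- *The exception allowing ineligible subjects to continue also biases toward safe, and contradicts 16.2.* Section 16.2 says "It is Sponsor policy that waivers to the clinical investigation plan will not be approved", but using an exception written into the plan is not a waiver of it. Ineligible eyes that are kept could look worse as easily as better.

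It is also fair that the plan defines no malposition proportion, so the arithmetic shows only what could happen.

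**Conclusion.** The point holds as a gap in a stated rule. The third exclusion in 8.3 can be met by a condition that is part of the outcome, and neither 9.4 nor 13.7 stops the affected eye from leaving the safety result. This is more than missing detail, because following the plan exactly as written permits an outcome-dependent exclusion.

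The size is unknown. Under the assumed range of 3 to 10 malpositioned eyes in 100, losing all of them gives a reported 0% with an upper limit between 3.7% and 4.0%. Losing about half of 5 or 10 roughly halves the estimate. These figures rest on the assumed rates, one implanted eye per patient and no replacement. The documents do not show that any such removal would take place. The change is worth making because it is cheap and protects the parameter closest to the device question.

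**What to change.** **Section 8.3.** Restrict the third exclusion to conditions documented in the preoperative or operative record, and specify them. Record eligibility from those records before the study measurements are made.

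**Section 13.7.** State that:

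- every examined eligible eye stays in the safety analysis;
- measurements made before any withdrawal are kept unless the subject objects;
- a lens-position finding after implantation is an outcome and not a ground for exclusion;
- every withdrawn or excluded subject is listed with the reason and any available lens-position and safety findings.

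**Section 9.4.** The investigator's freedom to stop examinations for a subject's sake can remain. A cross-reference to 13.7 makes clear that stopping examinations does not remove data already collected.

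**Cost.** Some rewording and a short record check per patient, with no added patients or visits. The reported malposition proportion may be less favourable.

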10 INVESTIGATIONAL DEVICE

10.1. Investigational device details

CT LUCIA hydrophobic C-loop IOL: CT Lucia® 601P

- Hydrophobic acrylic
- Heparin coated surface
- Preloaded system (avoiding contamination and minimizing risk of endophthalmitis)
- Off-label used for 'in the sulcus' implantation

Easy handling properties:

- unfolds very slowly after insertion in the eye: time for positioning IOL haptics

Perfect 'in the sulcus' design: good centration and positioning postoperative

- large optical part of ≥ 6 mm to avoid entrapment of the pupil behind the optic
- angulated IOL design that brings the optic backward to avoid contact with iris or entrapment of pupil
- IOL haptics make large contact between IOL and the sulcus

10.2. Device manufacturer

Carl Zeiss NV (Department in Belgium: [name])

10.3. Device accountability

In the hospital, there is a standard procedure for returning faulty products. This procedure will be followed, similar to the standard clinical path.

10.4. Storage conditions

All intra-ocular implant lenses are prepackaged in a sterile way. The CT Lucia 601 comes with a disposable preloaded system and are used before expiration date.

10.5. Concomitant Treatments

Not applicable

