11 CLINICAL INVESTIGATION ASSESSMENTS

11.1. Investigation Characteristics

❖ The following post-operative parameters will be collected:

- Indication of the surgery with implantation of the lens in the sulcus
- Refraction: objective and subjective
- Best Corrected Visual Acuity (BCVA)
- Pneumotonometry: intra-ocular pressure
- Biometry (using Zeiss IOLmaster 700 SS-OCT) to assess the position of the IOL in relation to the cornea (anterior chamber depth).
- Oculus Pentacam to determine IOL positioning relative to the iris
- SD-OCT: to assess the potential presence of macular edema and RNFL thinning
- Anterior chamber flare meter (Kowa) to determine the presence and quantification of any inflammation or pigment dispersion present in the anterior chamber
- Aberrometry to quantify HOA caused by IOL tilting/decentration

Note that all of the above investigation are non-contact measurements, hence without any risk of adverse events.

❖ Questionnaire about subjective quality of vision at least 6 months postop

- The patient will be asked to grade the quality of vision, at the time of completion, with a score of one to five according to the score system below:

- The questionnaire will be completed during the study visit

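### Treatment at the single visit is not recorded, so pressure, flare and macular edema readings mix treated and untreated eyes and probably understate problems in lens eyes

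*Combined protocol and SAP*

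**What the plan says.** Section 4 makes safety the primary question: "Primary endpoint: determine whether the CT Lucia 601 IOL can be used safely in the sulcus". Section 6 adds "The purpose of the study is to collect data that are parameters of post-IOL implantation safety", and its list includes anterior-chamber inflammation, intra-ocular pressure, macular edema, retinal nerve fiber layer (RNFL) thinning and "Any adverse ophthalmic events".

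The data come from one occasion: "A single late-postoperative visit, scheduled ≥ 6 months after the vitrectomy". Section 7 places this visit on top of the standard-of-care visits. Section 11.1 lists what is collected, including "Pneumotonometry: intra-ocular pressure" and "Anterior chamber flare meter (Kowa) to determine the presence and quantification of any inflammation or pigment dispersion present in the anterior chamber", together with SD-OCT. Neither current nor past eye medication is on that list.

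Section "10.5. Concomitant Treatments" consists of two words: "Not applicable". Section 8.3 excludes a history of uveitis but not glaucoma or the use of eye drops. Section 9.2 uses the fellow eye as control. Section 13 gives no rule for readings taken under treatment.

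**The concern.** Pressure, flare and macular edema can all be altered by treatment. By six months or later, a patient who developed one of these problems after sulcus implantation may well have been treated for it under standard care. If treatment is not recorded, a controlled eye and an eye that never had the problem give the same data. Such treatment is given mainly to eyes that had the problem, so the loss of information falls on the eyes that matter most to the safety question.

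The authors evidently had these complications in view: they measure flare and pressure, and their reference list contains a review of uveitis-glaucoma-hyphaema syndrome. A larger sample would not remove the distortion, and a statistical plan finalised later (section 13.6) cannot stratify on a variable that was not collected.

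**Working it through.** The plan states no figure that bears on this point: no cut-off for pressure or flare, no expected complication rate, no share of eyes on treatment. The check therefore has two parts: a reading of the text, and an illustration in which every rate is assumed.

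**1. Can the information be recovered elsewhere in the plan?**

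- *Section 6, adverse ophthalmic events.* A treated pressure rise would qualify, but no look-back period is given and section 11.1 has no matching data item.
- *Section 19.5, recording of safety issues.* The fields cover onset date, another suspect drug and the action taken. They apply to issues occurring during the clinical investigation, which for each patient is one visit. A condition still under treatment might be reported there; one treated months before and now controlled need not be.
- *Section 11.3, device incidents.* Reporting is at the investigator's discretion.
- *SD-OCT of the RNFL.* Existing thinning is not undone by drops, but section 11.1 lists no preoperative value, and the scan cannot show current treatment or treated inflammation.

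Each route is partial. None gives treatment status for every eye.

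**2. Lens eyes: illustration with assumed rates**

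Take n = 100 lens eyes (sections 8.1 and 13.2 differ on whether 100 is the total or the number per group), a true proportion p with raised pressure, and a share m of those brought down by treatment.

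Observed rate = p × (1 − m), with an exact (Clopper-Pearson) 95% interval.

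| p | m | Observed rate | 95% interval |
|---|---|---|---|
| 20% | 0 | 20% | 12.7% to 29.2% |
| 20% | 25% | 0.20 × 0.75 = 15% | 8.6% to 23.5% |
| 20% | 50% | 0.20 × 0.50 = 10% | 4.9% to 17.6% |
| 20% | 75% | 0.20 × 0.25 = 5% | 1.6% to 11.3% |
| 10% | 0 | 10% | 4.9% to 17.6% |
| 10% | 50% | 0.10 × 0.50 = 5% | 1.6% to 11.3% |

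A true 20% with half masked gives the same observed result as a true 10% with none masked. The planned data cannot separate the two.

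For mean pressure, understatement = share of eyes on treatment × average lowering. With assumed shares of 10% to 30% and lowering of 3 to 7 mmHg, the range runs from 0.10 × 3 = 0.3 mmHg to 0.30 × 7 = 2.1 mmHg. The midpoint case is 0.20 × 5 = 1.0 mmHg.

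**3. Fellow-eye comparison: which way does it move?**

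Assume true rates of 20% in lens eyes and 5% in fellow eyes, a true difference of 15 percentage points.

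- Half masked in lens eyes only: 10 − 5 = 5 points.
- Half masked in both: 10 − 2.5 = 7.5 points.
- Half masked in fellow eyes only: 20 − 2.5 = 17.5 points.

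The first two cases favour the lens and the third does not. The documents give nothing that selects among them.

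**The case against.** The strongest reply is that section 10.5 sits in the device chapter of a study with no study drug and no procedure, so its entry may mean only that no treatment is required or restricted. The eCRF forms (section 12.3) and Appendix B are not in view and might carry a medication field. This limits how firmly one can say that medication will not be collected. It does not supply the missing item in section 11.1 or the missing rule in section 13.

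A reader might infer that a controlled eye is recorded as normal and counted as safe. The plan does not say so. It sets no limit for pressure or flare and has no normal or safe category; it records the value and reports it descriptively. The accurate statement is that a treated reading cannot be distinguished from an untreated one.

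A reader might also infer that the complication vanishes from the study, or that the fellow-eye comparison must favour the lens. The first overlooks the adverse-event item in section 6, the action-taken field in section 19.5 and the RNFL measurement, which give partial capture. The second would need drops to be used mainly in the lens eye. The documents do not establish this, and since glaucoma is not excluded, earlier treatment may affect either eye.

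It is also fair to object to a primary outcome of abnormal or on new treatment. It could charge to the lens treatment that was prompted by the complicated cataract surgery, the vitrectomy or pre-existing disease. That objection stands, and it shapes the fix.

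**Conclusion.** The point holds in a limited form. Followed as written, the plan pools treated and untreated readings for three of its safety parameters, and the other provisions do not reliably identify the treated eyes. For lens eyes taken alone, the likely effect is to understate pressure, inflammation and edema problems. This rests on two assumptions: some lens eyes are on effective treatment at the visit, and no form outside the documents records it. For the fellow-eye comparison, the direction is uncertain.

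The size is unknown. The figures above show only that plausible-looking masking can halve an observed rate or move a mean by 0.3 to 2.1 mmHg; none is an estimate for this study. Since the study is exploratory and descriptive, and partial capture exists, this is a cheap improvement that should be made rather than a defect that invalidates the design.

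**What to change.** - **Section 10.5:** replace the present entry with a statement that eye treatment affecting the safety parameters will be recorded.
- **Section 11.1:** for both eyes, add pressure-lowering and anti-inflammatory treatment, current and since implantation, and any laser or surgery for pressure. Give each a start date relative to implantation and a reason.
- **Section 13:** report pressure, flare and macular edema separately for treated and untreated eyes. Beside the raw readings, report as a safety result the proportion of eyes with treatment started or increased since implantation. Show pre-existing treatment separately. A composite of abnormal or newly treated may be added as a supportive analysis.

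The cost is a few eCRF fields, filled from the hospital record and by questions at the existing visit. No examination is added and no patient's care changes. Histories will be incomplete for some referred patients, and complication rates may look less favourable.
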